## **9 TREATMENTS**

### **9.1 Investigational Therapy and Reference Therapy (Current Standard of Care)**

The investigational therapy ENVARSUS XR and TAC-IR will be provided by the patient's individual supply. The formulation for the investigational therapy is listed below.

**Study Drug:** ENVARSUS XR (tacrolimus extended-release tablets), once daily, for oral use; provided in 0.75 mg, 1.0 mg, and 4.0 mg dosage strengths.

## 9.2 Study Drug Dosing and Administration

ENVARSUS XR tablets will be administered orally q.d. in the morning based on a conversion factor from tacrolimus to ENVARSUS XR of 1:0.8 (see [Appendix 2 or https://www.envarsusxr.com/hcp/professional-resources/envarsus-xr-dose-converter/](https://www.envarsusxr.com/hcp/professional-resources/envarsus-xr-dose-converter/) and [PI discretion](#)) to maintain target trough level of 3-9 ng/mL. The following dosing instructions should be observed:

- Patients should take ENVARSUS XR on an empty stomach at the same time of the day, preferably in the morning (to ensure consistent and maximum possible drug exposure).
- Patients should swallow ENVARSUS XR whole with fluid (preferably water) and should not chew, divide, or crush the tablets.
- If a dose is missed, the patient should take it as soon as possible within 14 hours after the scheduled time and inform the study investigator; beyond the 14-hour time frame, the patient should wait until the usual scheduled time to take the next regular daily dose.
- Patients should avoid eating grapefruit or drinking grapefruit juice or alcoholic beverages while taking ENVARSUS XR.

Patients should be encouraged to take their study treatment on a consistent schedule with regard to time of day and relation to meals except on their study visit days. Patients will be instructed not to take their morning dose of TAC-IR prior to their clinic visit (Visit 2) but to take their morning concomitant medications as they normally would. Once at the clinic at Visit 2, after the TAC-IR trough level blood sample has been drawn, the patient will take the morning dose of TAC-IR. ENVARSUS XR will be prescribed, and patients will be instructed to begin taking ENVARSUS XR the following morning.

Likewise, for Visit 3, patients will be instructed not to take their morning dose of ENVARSUS XR prior to their clinic visit (Visit 3), after the ENVARSUS XR trough level blood sample has been drawn, the patient will take the morning dose of ENVARSUS XR.

For Visit 4, patients will be instructed not to take ENVARSUS XR before coming to the clinic; after their ENVARSUS XR trough blood draw and other procedures for the visit, they will take their last single daily dose of ENVARSUS XR.

## 9.3 Dose Adjustments

Patients who require a TAC-IR dose adjustment as a result of screening assessments are not to be considered stable and cannot enter the study, but may be re-screened up to 2 times after at least 4-7 additional days on stable dose of TAC-IR.

Dose adjustments of ENVARSUS XR are not permitted between Visits 2 and 3 unless it is deemed medically necessary at the discretion of the Investigator. If a dose adjustment is required the patient is required to be on a stable dose of ENVARSUS XR (no dose adjustment) for a minimum of 4 days before Visit 3 assessments are performed (i.e., if a dose adjustment is

medically necessary and occurs anytime between Visits 2 and 3 there should be a minimum of 4 days on a stable ENVARSUS XR dose before the Visit 3 assessments can take place). If multiple dose adjustments are required, the Investigator must first obtain Sponsor approval.

ENVARSUS XR dose adjustments to meet therapeutic range in ENVARSUS XR trough levels are permitted after Visit 3 per SOC. In these cases, ENVARSUS XR trough level should be measured, a safety assessment should be completed, and ENVARSUS XR should be dispensed (if applicable).

## **9.4 Concomitant Therapy**

### **9.4.1 Immunosuppressants**

Only CellCept® (MMF, Roche Laboratories, Nutley, NJ), Myfortic® (MPS, Novartis Pharmaceuticals, East Hanover, NJ), including generic versions of each, or prednisone (or equivalent <10 mg/day), with choice and doses per SOC at the participating site, are allowed (but not required). Patients receiving immunosuppressants should be on a stable dose throughout the treatment period from Visit 2 to Visit 3 of the study.

### **9.4.2 Drug Interactions**

Tacrolimus is metabolized by the CYP3A oxidase system. Substances which inhibit this enzyme can decrease metabolism and increase concentrations of tacrolimus, including study drug, and substances which induce CYP3A oxidase may increase metabolism and decrease blood concentrations (see [Appendix 1](#) for a partial listing of these medications). Whenever feasible, CYP3A inhibitors or inducers should be avoided, but clinical circumstances may necessitate using such agents. When this is the case, increased monitoring of tacrolimus concentrations is recommended.

Please consult the current prescribing information of MMF for drug interactions associated with MMF.

### **9.4.3 Other Medications**

All prophylaxis and other medications will be allowed per SOC at each of the participating sites as long as dosing remains stable throughout the treatment period Visits 1 – Visit3of the study.

## **9.5 Treatment Compliance**

Participants will be encouraged to bring their study medications to each study visit and reviewed by the research nurse with the participants.

.

## 10 STUDY VISITS AND ACTIVITIES

### 10.1 Study Activities by Visit

The specific study procedures to be performed at each visit are provided in the Schedule of Study Activities ([Table 3-1](#)). Permissible visit schedule changes are provided in [Section 10.1.7](#). Visits should be scheduled to coincide with SOC visits, where possible.

#### 10.1.1 Screening (Visit 1)

Prior to screening activities, each patient must be given an opportunity to ask questions and to understand the details of study participation. This consent process must be documented in the patient's source documents and evidenced by the patient signing the informed consent form (ICF). After signing the ICF, each patient will be assigned a patient identifier (PID) number that will be used on all patient documentation. PID numbers will be assigned in ascending sequential order.

Only patients who satisfy all of the inclusion and exclusion criteria specified in [Sections 8.2.1 and 8.2.2](#) will be eligible for entry into the study. If a patient's trough level is outside the 3-9 ng/mL range, the patient is not qualified for the study. All patients whose Visit 1 TAC-IR trough level is outside the 3-9 ng/mL range can be dose adjusted and re-screened up to 2 times (after at least 4-7 additional days on stable dose of TAC-IR).

Screening procedures and assessments will be conducted on Day -7 to -1. The Screening evaluations include the following:

- Assessment of entry criteria (including BDI-II).
- Recording of the patient's medical history.
- Urine pregnancy test (for female patients of child-bearing potential).
- Assessment of eGFR by MDRD4.
- Prior to the morning dose of TAC-IR, whole blood will be drawn to measure TAC-IR trough level (approximately 5 mL).
- Concomitant medication use (including an assessment of drug supply for each medication, including herbal products, to ensure adequate supply for the duration of the treatment phase) will be evaluated and recorded.
- .

Note that, in the event that screening laboratory results cannot be obtained on the same day as the visit to determine patient's eligibility for the study, the pregnancy and safety laboratory tests can be evaluated during the Day -7 to Day -1 time frame and the TAC-IR trough evaluation can be performed on Day -1. These evaluations do not need to be repeated at Visit 2 in these cases.

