d Whole blood for tacrolimus trough level (prior to the morning dose of tacrolimus) can be drawn on Day -1 such that the results are available for the determination of patient eligibility at Visit 2, in which case the draw does not need to be repeated at Visit 2.

e Pregnancy test must be completed for women of childbearing potential prior to enrollment.

f AE/SAE collection begins after the first dose of ENVARSUS XR.

g At enrollment patients should be prescribed a minimum of 4 months' supply; patients should be prescribed ENVARSUS XR at the end of Visit 3 (4-month supply), and/or SOC visit for ENVARSUS XR dose adjustment as needed.

h Patients will begin taking ENVARSUS XR as soon as possible but no later than the next 30 days.

i Labs should be charged to study if the visits don't coincide with standard of care of visits

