## 6 STUDY DESIGN

### 6.1 Overall Study Design

This is an open-label, single site, prospective Phase 4 clinical study to assess tacrolimus-induced cognitive impairment in stable kidney transplant patients converted from oral twice-daily TAC-IR to ENVARSUS XR once daily. Approximately 60 adult male or female patients who received a primary or secondary kidney transplant 4 weeks to 10 years prior to study start will be enrolled.

The study design is depicted in [Figure 6-1](#). Patients will be required to have been receiving a stable regimen of TAC-IR (i.e., no dose adjustments) for a minimum of 4-7 days prior to Baseline. At Baseline, patients will be switched to ENVARSUS XR for a total of 3 months.

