### **6.2.2 Secondary Efficacy Endpoints**

The secondary efficacy endpoints include the following:

- Change in cognitive function from Visit 2 to 3 as measured by the following:
- TMT-A and TMT-B (visual scanning speed/visual attention)
- Change in QoL from Visit 2 to 3 and from Visit 2 to 4 as measured by the WHODAS
- PGI-I and CGI-I at Visit 3
- Change in quality of sleep from Visit 2 to 3 as measured by the PIRS-20

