## **8.3 Interruption or Discontinuation of Treatment**

### **8.3.1 Withdrawal from Study**

1. Patients have the right to discontinue study treatment at any time for any reason without penalty or prejudice.
2. The Investigator also has the right to discontinue patients from study treatment if he/she feels it is in the best interest of the patient.
3. A patient may be withdrawn from the study treatment by the Investigator if: (1) the Investigator feels it is not in the patient's best interest to continue in the study, (2) the

patient fails to follow the Investigator's instructions, (3) the patient experiences an adverse reaction that requires other medical treatment, or (4) the patient becomes pregnant.

In the absence of a medical contraindication or significant protocol violation, every effort should be made by the Investigator to keep the patient in the study. Should a patient not complete the study, the patient should complete all the procedures outlined under early withdrawal in the Study Schedule (refer to **Table 3-1**). Reasons for discontinuation will be documented on the case report forms (CRFs).

If, in the opinion of the Investigator, the clinical observations in the study suggest that it may be unwise to continue, the Investigator may suspend or terminate the study.

A written statement will be provided to the Institutional Review Board (IRB) and regulatory authorities, if required.

All patients whose Visit 1 TAC-IR trough level is outside the 3-9 ng/mL range can be rescreened up to 2 times after at least 4-7 additional days on stable dose of TAC-IR.

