#### 10.1.2 Enrollment (Visit 2)

Note that the designation of Visit 2 as occurring on 'Day 0' is meant to reflect that ENVARSUS XR dosing is to start as soon as possible but no later than the next 30 days. Visit 1 and Visit 2 may be combined if no dose adjustments were performed and the patient has been maintained on a

stable dose of TACIR with trough level between 3-9 ng/mL, and the physician does not deem any dose adjustment required.

Upon arrival at the clinic at Visit 2 the following assessments will be performed:

- Prior to the morning dose of TAC-IR, the patient will have approximately 5 mL of whole blood drawn for the assessment of TAC-IR trough.
- After confirmation of patient eligibility, a blood drawn for safety laboratory parameters (approximately 15 mL, for complete blood count [CBC] and a metabolic profile [blood glucose, calcium, sodium, potassium, CO2 (carbon dioxide, bicarbonate), chloride, blood urea nitrogen (BUN) and creatinine]).
- Physical examination and vital signs measurements.
- Patients will then be instructed to take their morning dose of TAC-IR.
- QoL and cognitive tests will then be performed after the morning TAC-IR dose in the following order:
  - WHODAS; ○ PIRS-20; ○ RBANS, ○ TMT-A and TMT-B;
  - After cognitive tests, ENVARSUS XR will be prescribed and patients will be instructed to take the first dose of ENVARSUS XR as soon as possible but no later than the next 30 days . Patients must be instructed to take their evening dose of TAC-IR.
- Concomitant medication use (including compliance to immunosuppressive therapy and adequate drug supply) and the safety monitoring processes will be initiated.
- Prior to leaving the clinic, the patient will be prescribed ENVARSUS XR with instructions to take the medication as soon as possible but no later than the next 30 days prior to noon each day for the remainder of the study. Patients will be reminded not to take their daily dose of ENVARSUS XR prior to their clinic at Visit 3 and to bring all remaining ENVARSUS XR medications to that visit.

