#### **10.2.2.4 Pittsburgh Insomnia Rating Scale (PIRS-20)**

The PIRS-20 is the short version of the original PIRS, both copyrighted by the University of Pittsburgh. The original PIRS is a 65-scale item, widely used instrument in clinical and research practice. It was designed to rate the severity of insomnia in clinical trials and clinical practice. Domains of the PIRS-20 include subjective distress (12 items), subjective sleep parameters (4 items) and quality-of-life (4 items). The recall period of the PIRS-20 is the past 7 days. The PIRS-20 total score is the sum of all items and ranges from 0 (good sleep) to 60 (bad sleep). The PIRS-20 should be administered following the WHODAS at Visit 2 and Visit 3. Administration time: approximately 5-10 minutes.

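### After a TAC-IR dose change at re-screening, Visit 2 can fall on about day 5, so the 7-day PIRS-20 baseline recall can include about two days on the old dose; the bias is probably small and cheap to prevent

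*Combined protocol and SAP*

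**What the plan says.** Three places govern re-screening. Section 10.1.1: "All patients whose Visit 1 TAC-IR trough level is outside the 3-9 ng/mL range can be dose adjusted and re-screened up to 2 times". Section 8.3.1 says that patients with an out-of-range trough "can be rescreened up to 2 times after at least 4-7 additional days on stable dose of TAC-IR". Section 9.3 says that patients who need a TAC-IR adjustment as a result of screening cannot enter as they stand but "may be re-screened up to 2 times after at least 4-7 additional days on stable dose of TAC-IR". All three give the stable period as a range, not a single minimum.

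The gap from re-screen to baseline can be short. Table 10-1 places screening 1 to 30 days before enrollment; Section 10.1.1 uses Day -7 to -1. Footnote d of the Schedule of Study Activities says that the trough sample "can be drawn on Day -1 such that the results are available for the determination of patient eligibility at Visit 2". Same-day screening and enrollment is closed to adjusted patients: "Visit 1 and Visit 2 may be combined if no dose adjustments were performed" (Section 10.1.2).

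The PIRS-20 is completed at Visit 2, and "The recall period of the PIRS-20 is the past 7 days" (Section 10.2.2.4). One secondary endpoint is "Change in quality of sleep from Visit 2 to 3 as measured by the PIRS-20" (Section 6.2.2). Section 14.3.3 takes baseline as the last value before the first ENVARSUS XR dose, without a condition on recent TAC-IR changes. Sections 14.2 and 14.5.2 neither exclude nor separate patients adjusted shortly before baseline. Section 14 defers a full SAP to a later date.

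**The concern.** The study has no control arm. Section 7 relies on each patient serving as his or her own control, so anything that distorts the baseline goes straight into the reported change. Section 4.6 lists insomnia among the most often documented neurotoxic effects of tacrolimus, and a higher PIRS-20 score means worse sleep.

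Take a patient whose TAC-IR dose is lowered because the screening trough exceeded 9 ng/mL. If Visit 2 follows within days, the baseline PIRS-20 partly describes sleep on the higher dose. Any improvement due to the TAC-IR reduction then appears in the Visit 2 to Visit 3 change and is credited to ENVARSUS XR. An upward adjustment after a trough below 3 ng/mL works the other way.

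**Working it through.** **Plan's own figure.** The 34 evaluable patients (Section 14.1: effect size 0.5, 80% power, one-sided 0.025) reproduce with a paired t-test: power is 0.795 at n=33 and 0.808 at n=34. This figure does not bear on the timing question. The plan's maximum of 52 is used below.

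**Step 1: earliest Visit 2.** Count the first day on the new TAC-IR dose as day 0. Lower bound of the stable period, 4 days, plus the minimum gap from re-screen to enrollment, 1 day: 4 + 1 = day 5.

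**Step 2: recall days on the old dose.** With Visit 2 on day v, the preceding 7 days contain max(0, 7 - v) old-dose days.

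| Visit 2 | Old-dose days, visit day not counted | Visit day counted |
|---|---|---|
| Day 5 | 2 of 7 (29%) | 1 of 7 (14%) |
| Day 6 | 1 of 7 (14%) | 0 |
| Day 7 or later | 0 | 0 |

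Section 10.2.2.4 does not say whether the visit day counts.

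**Step 3: concentration carry-over.** The Excretion part of Section 12.3 of the prescribing information (Appendix 3) gives half-lives of 31.0 h (repeated ENVARSUS XR dosing) and 48.4 h (radiolabelled oral tacrolimus), both in healthy subjects. With k = ln 2 × 24 / half-life, k is 0.537 or 0.344 per day. The share of the old-to-new step remaining, averaged over a 7-day recall ending on day d, is

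- d < 7: [(7 - d) + (1 - exp(-kd))/k] / 7
- d ≥ 7: [exp(-k(d - 7)) - exp(-kd)] / (7k)

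Results (31.0 h, 48.4 h): day 5, 0.534 and 0.627; day 7, 0.260 and 0.378; day 14, 0.006 and 0.034.

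**Step 4: size of the bias.** These inputs are assumptions that the documents do not give: 30% of patients adjusted, all downward; full gain 0.5 SD of the change score; effect proportional to concentration; half-life 48.4 h; one-sample t-test on the PIRS-20 change, two-sided 5%, n=52. The shift in the mean is 0.30 × 0.5 × averaged step, and the rejection rate comes from the noncentral t distribution.

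| When adjusted patients have Visit 2 | Averaged step | Shift (SD) | Rejection rate |
|---|---|---|---|
| Evenly over days 5-34 (Table 10-1 window) | 0.081 | 0.012 | 5.1% |
| Evenly over days 5-11 (Section 10.1.1 window) | 0.314 | 0.047 | 6.3% |
| All on day 5 | 0.627 | 0.094 | 10.2% |

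The even spread is itself illustrative. At milder inputs (10% adjusted, 0.3 SD, 31.0 h), all on day 5, the shift is 0.10 × 0.3 × 0.534 = 0.016 SD and the rate 5.1%. With the worst inputs on day 5 but one third of adjustments upward, the rate is 5.6%; with equal directions the bias cancels.

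**Step 5: RBANS.** A performance test has no recall window, so only the residual on the day counts: 0.5^(120/48.4) = 0.179. The shift is at most 0.15 × 0.179 = 0.027 SD, a rate of 5.4% with all adjusted patients on day 5.

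**The case against.** The best reply is that the case needs several things to coincide. Visits are meant to follow standard-of-care appointments where possible, and the windows run to 7 or 30 days after screening, so few adjusted patients need be tested at the minimum interval. The re-screen trough must itself be 3-9 ng/mL. Sections 4.2 and 4.6 say that neurotoxicity follows troughs poorly and peaks better, which weakens the proportionality assumption. Section 14.5.2 names no test for PIRS-20. The screening trough usually shows which way the dose was moved, so the records are not blank. The endpoint is one secondary scale in an exploratory study. All of this stands, and it limits the size of the problem. It does not remove it: the rule as written still permits day 5, and no stated analysis would show it.

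Three stronger readings are tempting and are not supported.

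- **Visit 2 on day 4, with 3 of 7 recall days on the old dose.** A reader might infer this from Section 6.1, which asks for a "stable regimen of TAC-IR (i.e., no dose adjustments) for a minimum of 4-7 days prior to Baseline". That is a general design summary for all patients. The specific rules put the re-screen after the stable days, require at least one day to enrollment, and bar combined visits after an adjustment.
- **A false-positive rate of 10% or more as the expected outcome.** The 10.2% figure needs every adjusted patient on day 5, every change downward, and the largest assumed share and gain.
- **An overlap that is certain.** It depends on how the range is read and when Visit 2 is booked, and may be zero.

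**Conclusion.** The point holds as a modest one. At its lower bound, the re-screening rule lets the PIRS-20 baseline of a dose-adjusted patient include about 2 of 7 days (1 if the visit day is counted) on the previous TAC-IR dose, and the stated analyses do not separate such patients. The day count rests on the text alone. The effect on the result rests on assumed inputs, because the documents give neither the number nor the direction of adjusted re-screens. Even with unfavourable inputs, the nominal 5% test moves only to about 5.1-6.3% at n=52 when visits spread over the permitted windows. The bias is therefore probably small, and the primary RBANS comparison is not materially affected. It is worth correcting because the correction is nearly free, not because the result is in danger.

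**What to change.** Add one sentence to Sections 8.3.1, 9.3 and 10.1.1, for dose-adjusted re-screens only: *After any TAC-IR dose adjustment, Visit 2 testing takes place no earlier than 7 days after the last change.*

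This removes every old-dose day from the PIRS-20 recall and settles the four-to-seven-day ambiguity for these patients. It does not remove all concentration carry-over: on the half-lives above, 26-38% of the step remains on average over the recall at day 7, and nearly eliminating it would take about 14 days. The entry criterion for unadjusted patients can stay as it is.

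The cost is a delay of a few days for a few patients. The sentence fits the existing windows: a re-screen trough on days 4-6 with Visit 2 on day 7 falls on Day -3 to -1, inside both the Day -7 to 0 trough rule and the 1-30 day screening window. Recording the date and direction of the change, and tabulating results with and without these patients, would add little and is optional.

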#### 10.1.2 Enrollment (Visit 2)

Note that the designation of Visit 2 as occurring on 'Day 0' is meant to reflect that ENVARSUS XR dosing is to start as soon as possible but no later than the next 30 days. Visit 1 and Visit 2 may be combined if no dose adjustments were performed and the patient has been maintained on a

stable dose of TACIR with trough level between 3-9 ng/mL, and the physician does not deem any dose adjustment required.

Upon arrival at the clinic at Visit 2 the following assessments will be performed:

- Prior to the morning dose of TAC-IR, the patient will have approximately 5 mL of whole blood drawn for the assessment of TAC-IR trough.
- After confirmation of patient eligibility, a blood drawn for safety laboratory parameters (approximately 15 mL, for complete blood count [CBC] and a metabolic profile [blood glucose, calcium, sodium, potassium, CO2 (carbon dioxide, bicarbonate), chloride, blood urea nitrogen (BUN) and creatinine]).
- Physical examination and vital signs measurements.
- Patients will then be instructed to take their morning dose of TAC-IR.
- QoL and cognitive tests will then be performed after the morning TAC-IR dose in the following order:
  - WHODAS; ○ PIRS-20; ○ RBANS, ○ TMT-A and TMT-B;
  - After cognitive tests, ENVARSUS XR will be prescribed and patients will be instructed to take the first dose of ENVARSUS XR as soon as possible but no later than the next 30 days . Patients must be instructed to take their evening dose of TAC-IR.
- Concomitant medication use (including compliance to immunosuppressive therapy and adequate drug supply) and the safety monitoring processes will be initiated.
- Prior to leaving the clinic, the patient will be prescribed ENVARSUS XR with instructions to take the medication as soon as possible but no later than the next 30 days prior to noon each day for the remainder of the study. Patients will be reminded not to take their daily dose of ENVARSUS XR prior to their clinic at Visit 3 and to bring all remaining ENVARSUS XR medications to that visit.

